5.0 Analysis of Safety

All safety analyses will be performed on the Safety Population.

The safety analysis variables are defined as follows:

- Adverse Events (AEs)
- Clinical Laboratory Tests (hematology, serum chemistry, urinalysis, RA panel)
- ECG Parameters
- Vital Signs

Adverse Events

Adverse events will be observed for each patient from signing of informed consent until termination from the study. AEs will be coded using the Medical Dictionary for Regulatory Activities (MedDRA[®]). A treatment-emergent AE (TEAE) is defined as an AE whose start date is on or after the initial procedure date. Based on the coded terms, frequencies of each TEAE will be summarized by MedDRA[®] preferred term within system organ class (SOC), by severity grade, and by relationship to Tc 99m tilmanocept.

A summary of TEAEs will be constructed showing the following:

- Number of patients with at least one TEAE
- TEAEs by severity grade
- TEAE by relationship to Tc 99m tilmanocept
- TEAEs by relationship of TEAE to study procedure
- Number of patients with at least one treatment emergent serious adverse event

Treatment-emergent serious adverse events (TESAEs) will be tabulated by MedDRA[®] preferred term within SOC.

A by-patient AE data listing of all AEs including verbatim term, coded term, grade, and relation to study drug will be provided.

Clinical Laboratory Tests

Clinical laboratory tests will be performed at screening (baseline) and after the image acquisition on each imaging day (Visits 2, 4, 6, and 8). Only RA panel lab values and abnormal clinical laboratory values will be assessed for clinical significance as applicable. For each quantitative laboratory test, summary statistics (mean, standard deviation, median, range, n) on the raw as well as their changes from baseline will be presented by timepoint. A shift table will also be produced to show the changes in lab values over time relative to the normal ranges.

If multiple labs were performed at a given visit, then the latest results will be summarized in the analysis tables. All collected lab data will be listed.

ECG Parameters

ECGs will be performed within 30-minutes before and after injection. For each ECG parameter (heart rate, QRS, QT, PR, and QTcF), summary statistics (mean, standard deviation, median, range, n) on the raw as well as their changes from baseline will be presented by timepoint. A shift table will be provided to show changes in the qualitative assessment (abnormal or normal) from baseline (pre-injection) to post-injection. The baseline value for each of the post-injection ECG parameters will be the corresponding pre-injection time point. All ECG data will be listed.

Vital Signs

Vital signs will be performed at screening and within 30-minutes before and after injection. Height and weight will be measured only at screening and will be summarized as part of the baseline and demographic information. For each vital sign (respiration rate, systolic blood pressure, diastolic blood pressure, heart rate and temperature), summary statistics (mean, standard deviation, minimum, maximum, n) on the raw as well as their changes from baseline will be presented by timepoint. The baseline value for each of the post-injection vital sign parameters will be the corresponding pre-injection time point. If there are multiple vital signs taken at any time point, then the latest set of vital signs will be used for the analysis. All vital sign data will be listed.

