	• To evaluate the negative predictive value (NPV) of TUV_{global} obtained before initiation of anti-TNF α therapy ($TUV_{global[b]}$) relative to a clinical non-response to therapy at 24 weeks.		
	Secondary		
	• To evaluate the sensitivity and specificity of TUV _{global} obtained before initiation of anti-TNFa therapy and at 5 weeks ± 1 week following change in therapy relative to a positive clinical response or a non-response to therapy at 12 weeks.		
	• To evaluate the NPV of TUV _{global[b]} relative to a clinical non-response to therapy at 12 weeks.		
	• To evaluate the positive predictive value (PPV), negative predictive value (NPV), and overall accuracy (OA) of TUV _{global} obtained before initiation of anti-TNFα therapy and at 5 weeks ± 1 week (ΔTUVglobal _[5w]) following change in therapy relative to a positive clinical response or a non-response to therapy at 12 and/or 24 weeks.		

Confidential Page 7 of 89

Dose(s) and Route of administration	Dose: Tilmanocept will be administered at a mass dose of 150 mcg radiolabeled with 10 mCi Tc 99m. Route of Administration: Tc 99m tilmanocept will be administered through an intravenous (IV) route of administration using a single syringe injected as a slow IV push. The preferred site of IV placement will be the left or right antecubital vein. At the completion of Tc 99m tilmanocept administration, a 10 mL sterile normal saline flush will be administered.		
Study drug	Technetium Tc 99m tilmanocept		
Duration of treatment	24 ± 1 weeks; Tc 99m tilmanocept will be administered at baseline and at Week 5. Tilmanocept will also be administered to a subset of subjects at weeks 12 and 24 (those enrolled and completing Weeks 12 and 24 prior to activation of Amendment 4).		
	 To evaluate sensitivity and specificity in patient subgroups. To evaluate the safety of IV-administered tilmanocept radiolabeled with Tc 99m. 		
	To evaluate the correlation of changes with TUV _{global} and changes in clinical RA assessments as a means to monitor therapy. The state of the correlation of changes with TUV _{global} and changes in clinical RA assessments as a means to monitor therapy.		
	• To evaluate the correlation of changes in TUV _{global} obtained before initiation of anti-TNFα therapy and at 5 weeks ± 1 week following a change in therapy with changes in clinical assessments at 12 and/or 24 weeks for specific anti-TNFα bDMARD agents.		

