3.3 Study Duration

Subjects will be "on study" for up to 213 days depending on the duration of the screening window (up to 30 days).

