7.2.2.2 Administration of Tc 99m Tilmanocept

IV administration of Tc 99m tilmanocept will be at study time 00:00. The preferred site of IV placement will be the left or right antecubital vein.

The pre-filled syringe will be connected to a catheter for a slow push injection. At the completion of the injection, a 10-mL sterile normal saline flush will be administered. The IV administration will be performed in the nuclear medicine department by an onsite Certified Nuclear Medicine Technologist or Nuclear Medicine Physician. Subjects will be continuously monitored for adverse events.

7.2.2.3 0 to 30 Minutes After Tc 99m Tilmanocept Administration

- Assessment of adverse events
- Vital signs after at least 1 minute in a resting position (body temperature, heart rate, blood pressure, and respiratory rate)

7.2.2.4 60 to 75 Minutes After Tc 99m Tilmanocept Administration

- Assessment of adverse events
- Image acquisition: planar scan of bilateral hands and wrists
- Clinical labs (within 60 minutes after the completion of imaging)
- Urinalysis (within 60 minutes after the completion of imaging)

Upon the completion of all Visit 2 procedures, subjects will initiate their new anti-TNFa bDMARD treatment regimen. The exact agent, dose, start date, and planned dosing frequency will be documented. For each subsequent administration, the following details will be documented:

- 1. Administration start time
- 2. Administration end time
- 3. Total volume injected
- 4. Total dose administered

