8.5 Adverse Events

8.5.1 Definition of Adverse Event

The definitions below follow International Conference on Harmonization (ICH) – Good Clinical Practice (GCP) (see also ICH E2A Guideline for Clinical Safety Data Management: Definitions and Standards for Expedited Reporting).

Adverse Event (AE)

An AE is defined as any untoward medical occurrence in a subject administered a pharmaceutical product and which does not necessarily have a causal relationship with this

treatment. An AE can therefore be any unfavorable and unintended sign (including an abnormal laboratory finding), symptom, or disease temporally associated with the use of a medicinal (investigational) product, whether or not considered related to the medicinal (investigational) product.

Any clinically significant change in a condition (worsening) from screening that results in a change in subject management will be considered an AE and will be recorded on the AE page of the CRF.

By definition for this study, all untoward medical occurrences beginning on the day of Visit 2 Baseline (Day 0) through the final visit (Visit 8) are to be reported as AEs. AEs continuing after study completion will be followed to normalization or stabilization. Additionally, untoward medical events occurring prior to the day of Tc 99m tilmanocept administration will be collected and added to the subject's medical history unless they are related to a study procedure in which case the event will be recorded as an AE. SAEs will be reported from the time of consent through the end of participation.

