8.5.3 Assessments and Documentation of Adverse Events

Attention shall be paid to the occurrence of AEs for the duration of subject participation. Events occurring prior to Visit 2 (day of Tc 99m tilmanocept administration) will be recorded in the subject's medical history. Untoward medical events beginning on Visit 2 (day of Tc 99m tilmanocept administration) through the completion of Visit 8 will be reported as adverse

events. Thus, subjects should be closely observed by the investigator both during and after the evaluation.

Any AE (observed, volunteered, or elicited) should be recorded in detail in the source documentation.

The following information is required:

- The date and time of onset of any AE.
- The duration (the entire duration of an event or symptom, calculated from date of onset to date of end, if not recorded directly).
- The seriousness of the AE will be assessed by the investigator. If the investigator deems that an AE qualifies as an SAE, a special form provided by the sponsor should be completed and the event must immediately, and within one day (i.e., within 24 hours) of becoming aware of the SAE, be reported to the sponsor. A definition of serious adverse events is provided in Section 8.5.5.
- The maximum intensity (mild, moderate, or severe).
- Whether drug treatment was administered for the event, any specific drug treatment must be documented.
- The relationship of the AE to the investigational product and to study conduct (for definitions, see above).
- The **outcome** of the AE (resolved, resolved with sequelae, not resolved, unknown, death).

AEs will be coded according to an internationally recognized dictionary (Medical Dictionary for Regulatory Activities [MedDRA]).

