9.5.4 Analysis of Safety Variables

All safety analyses will be conducted on the safety population.

All AEs will be observed for each subject from the time of signing of informed consent until study completion. A treatment-emergent AE (TEAE) is defined as an AE whose start date is on or after the initial procedure date. If the procedure date or the AE start date is missing, the AE will be considered treatment emergent.

Prior to analysis all AEs will be coded using the MedDRA coding dictionary. Based on the coded terms, TEAEs will summarized by cohort and overall as follows:

- By system organ class (SOC) and preferred term (PT);
- By SOC and PT and relation to the study drug;
- By SOC and PT and severity.

Observed and change from baseline vital sign parameters, ECG parameters, and hematology, clinical chemistry and urinalysis parameters will be summarized using descriptive statistics (mean, standard deviation, median, and range) at each time point.

Other safety analyses may be described in the SAP for the study.

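### TEAEs run from an undefined start date to Week 24 with no end, and no planned summary shows adverse events by time since tilmanocept injection

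*SAP*

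**What the plan says.** **Objective and exposure.** Protocol 2.3 lists the safety of IV tilmanocept as a secondary objective. On exposure, the Protocol synopsis states: "Tc 99m tilmanocept will be administered at baseline and at Week 5". It adds: "Tilmanocept will also be administered to a subset of subjects at weeks 12 and 24". That subset is the patients who completed those visits before Amendment 4 took effect. SAP 1.2 still describes injections at Weeks 5, 12 and 24.

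**Other treatment.** Protocol 7.2.2.4 states: "Upon the completion of all Visit 2 procedures, subjects will initiate their new anti-TNFa bDMARD treatment regimen". The actual start date is recorded. The study is open-label and not randomized (Protocol 9.1), with no control arm.

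**TEAE rule.** SAP 5.0: "A treatment-emergent AE (TEAE) is defined as an AE whose start date is on or after the initial procedure date". Protocol 9.5.4 carries the same sentence and adds: "If the procedure date or the AE start date is missing, the AE will be considered treatment emergent". The SAP does not repeat that addition. Neither document says which procedure is meant or when the period ends. Protocol 8.5.1 has AEs reported from the day of Visit 2 through Visit 8 (Week 24 ± 1).

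**Onset time.** Protocol 8.5.3 requires: "The date and time of onset of any AE".

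**Planned outputs.** Table 39 (TEAEs), Table 41 (TESAEs) and Table 42 (by severity) have no split by relationship or by timing. Table 40 gives each patient's highest relationship to tilmanocept and to the study procedure. Table 43 gives each event term at five levels of relationship to tilmanocept. Listing 11 prints, for each event, the start of the nearest previous injection.

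**The concern.** The question for this agent is what happens after an injection. Under the rule as written, an event in Week 20, about 15 weeks after the Week 5 injection, counts the same as one an hour after injection. With no control arm, the usual way to tell a drug effect from background is to look at how events cluster in time around dosing. No planned table does that, and none is split by injection.

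What remains is the causality rating. It is given by an open-label investigator, and Protocol 8.5.2 asks for it only against tilmanocept and the study procedure. The anti-TNF drug has no rating of its own.

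There is also a small fault at the start of the period. AEs are assessed on Day 0 before the injection (Protocol 7.2.2.1 and the Schedule of Events). Because the rule compares dates only, an event that began that morning before the injection is treatment-emergent, although its onset time is on record.

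At stake is how well a stated safety objective is answered. The co-primary endpoints are not affected.

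**Working it through.** The documents give no AE rate and no TEAE window length, so there is no planned figure to reproduce. The check asks how much of the TEAE period lies near an injection.

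**Inputs**
- Follow-up from Day 0 to Visit 8: 24 weeks = 168 days (161 to 175 days with the ± 1 week).
- Injections: 2 under the current schedule; 4 in the earlier subset.
- Window: the safety telephone contact is 5 ± 3 days after the imaging visit (Protocol 7.2.3 and 7.2.5), so at most 8 days.
- Mean blood half-life (Protocol Table 2): 719.1 min in RA and 759.0 min in healthy controls, from 6 subjects each at 400 mcg.

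**Step 1. Share of follow-up inside 8-day windows** = injections × 8 / follow-up days.
- Two injections: 2 × 8 / 168 = 9.5%, so 90.5% lies outside. Over 161 to 175 days the inside share is 9.9% to 9.1%.
- Counting the injection day as a day of its own: 2 × 9 / 169 = 10.7%.
- Four injections, assuming follow-up ran 8 days past the Week 24 injection: 4 × 8 / (168 + 8) = 32 / 176 = 18.2%, so about 82% lies outside.

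**Step 2. A shorter, pharmacokinetic window.** Five half-lives (an assumption) are 5 × 719.1 min = 59.9 h, or 5 × 759.0 min = 63.3 h. Two such windows in 168 × 24 = 4,032 h are 2 × 59.9 / 4,032 = 3.0% and 2 × 63.3 / 4,032 = 3.1%. The 8-day window is therefore the generous choice.

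**Step 3. From time to events.** If background events arise at a constant rate (assumption), the share of them outside the windows equals the share of time outside: about 90% for two injections and 82% for four.

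**Step 4. From events to patients.** The tables count patients. If a share b of patients has at least one background event over 24 weeks, the share with one inside the two 8-day windows is 1 − (1 − b)^(16/168). The documents give no value for b, so a range is assumed.

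| b over 24 weeks (assumed) | Share with an event inside the windows |
|---|---|
| 30% | 3.3% |
| 50% | 6.4% |
| 70% | 10.8% |

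Over this range, restricting to the windows lowers the background against which an injection effect must be seen from 30-70% of patients to about 3-11%.

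**The case against.** **The plan already separates events by relationship.** This is true. The sentence after the definition in SAP 5.0 plans frequencies by relationship to tilmanocept, and Tables 40 and 43 deliver them. A reader might infer that the safety tables cannot describe tilmanocept at all. The documents do not support that. These splits reduce the problem, but they rest on case-by-case judgement, and a summary by timing would be the check on that judgement.

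**Timing is not ignored.** Listing 11 sets each event beside the nearest previous injection, and vital signs are compared before and after each injection (SAP 5.0, Table 52). Both points stand. A listing is not a frequency, however, and vital signs cover only 30 minutes on either side.

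**A specific reaction is not diluted.** Table 39 has a row per preferred term, so injection-site pain is not hidden by infections in other rows. This stands. Mixing affects the any-TEAE and any-TESAE lines and common, non-specific terms. *Treatment-emergent* is also a timing label and does not attribute an event to tilmanocept.

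**The inclusive count is the cautious one.** This also stands. Replacing Tables 39-43 with windowed versions would take late serious events out of the main tables.

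**A window does not remove the confounding.** The Day 0 window also covers the first days of anti-TNF treatment. That is correct, and it is why the display should be by injection number.

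**Conclusion.** The point holds as a gap in the safety summaries. The TEAE rule is open-ended, works on dates only and starts at an undefined procedure. No planned summary gives event frequency by time since injection. About 90% of follow-up under the two-injection schedule, and about 82% for patients with four injections, lies outside any 8-day post-injection window. Reading those shares as shares of background events needs a constant background rate. If such events cluster soon after the anti-TNF drug starts, more of them fall in the Day 0 window.

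A reader might go further and infer that the tables mainly measure the anti-TNF drug and the underlying RA. The documents give no event rates for either, and intercurrent illness and other medicines contribute too, so *background events* is as far as the text allows. A reader might also take the anti-TNF start to be always on Day 0. The protocol places it after the Day 0 procedures and records the date, without fixing the day.

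The co-primary endpoints are untouched. This is a cheap improvement to how a secondary objective is answered.

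**What to change.** 1. In SAP 5.0 and Protocol 9.5.4, define the initial procedure as the date and time of the first tilmanocept injection. A Day 0 event with a known onset time before the injection is then not treatment-emergent. Carry the protocol's missing-date rule into the SAP, and extend it to a Day 0 event with no onset time, so that such events still count.
2. Keep Tables 39-43 as they are, labelled as inclusive tables from Day 0 to Week 24, so that late serious events stay in the main output.
3. Add supplementary TEAE and TESAE tables restricted to onset from each injection through the end of the 5 ± 3 day telephone window (day 8). Present them by injection number, with the patients given that injection as the denominator. This also separates the Week 12 and Week 24 injections of the earlier subset.
4. State in a footnote that the Day 0 window overlaps the start of the anti-TNF drug, and that the Week 5 window is less affected by treatment initiation.

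The cost is a few sentences in two documents and one extra set of table shells. No new data are needed: onset date and time are collected, and Listing 11 already calls for the time of the nearest previous injection.

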6.0 Other Relevant Data Analyses/Summaries

6.1 Patient Completion

A table will be constructed with counts of screen failures and enrolled patients. Of those enrolled, counts and percentages of patients withdrawing from the study before study completion and the number completing the study will be displayed. For those patients that withdraw before completion of the study, counts and percentages of the reasons for withdrawal will be tabulated. A data listing of all patient completion and withdrawal data will also be constructed.

6.2 Physical Exam

Physical exams will be performed at screening. All physical exam data will be listed.

6.3 Study Drug Administration

The volume, the calculated mass dose, and radioactivity of Tc 99m tilmanocept injected will be summarized. All study drug administration data will be listed.

6.4 RA Evaluation and Screening Physical Exam

Each RA patient will undergo a DAS28 evaluation during screening and at weeks 5, 12, and 24. The swollen and tender joints will be identified and documented during the physical examination. Results of all DAS28 evaluations will be listed.

6.5 Concomitant Medications

All prior and concomitant medications will be listed, as shown in Appendix B. A separate data listing will be created to show only those medications that were taken for RA.

7.0 List of Analysis Tables, Figures and Listings

Table No.	Table Title	Included in Final Tables	Shown in Appendix B
1	Patient Disposition	X	X
2	Demographics and Baseline Data Summary Statistics -	X	X
-	Continuous Variables (Safety Population)		
3	Demographics and Baseline Data Summary Statistics-	Х	Х
	Categorical Variables (Safety Population)		
4	Summary of Study Drug Administration (Safety Population)	Х	Х
5	Summary of TUV by Study Day and DAS28 Joint (ITD population)	X	Х
6	Summary of TUV by Study Day and DAS28 Joint (PP Population)	X	
7	RA Status Summaries (ITD Population)	Х	Х
8	RA Status Summaries (PP Population)	Х	
9	ACR Response Classification by Time Point (ITD Population)	Х	Х
10	ACR Response Classification by Time Point (PP Population)	X	
11	Concordance of TUV _{global[b]} Alone and of Δ TUV _{global[5w]} Bucketing and Week 12 Clinical Improvement Criteria (ITD Population)	X	Х
12	Concordance of TUV _{global[b]} Alone and of ∆TUV _{global[5w]} Bucketing and Week 12 Clinical Improvement Criteria (PP Population)	X	
13	Concordance of TUV _{global[b]} Alone and of ∆TUV _{global[5w]} Bucketing and Week 24 Clinical Improvement Criteria (ITD Population)	X	
14	Concordance of TUV _{global[b]} Alone and of ∆TUV _{global[5w]} Bucketing and Week 24 Clinical Improvement Criteria (PP Population)	X	
15	Concordance of $\Delta TUV_{global[12w]}$ Bucketing and Week 24 Clinical Improvement Criteria (ITD Population)	Х	X
16	Concordance of $\Delta TUV_{global[12w]}$ Bucketing and Week 24 Clinical Improvement Criteria (PP Population)	Х	
17	Concordance of $\Delta TUV_{global[5w]}$ Bucketing and Week 12 Clinical Improvement Criteria in Subgroups (ITD Population)	Х	X
18	Concordance of ∆TUV _{global[5w]} Bucketing and Week 12 Clinical Improvement Criteria in Subgroups (PP Population)	Х	
19	Concordance of $\Delta TUV_{global[5w]}$ Bucketing and Week 24 Clinical Improvement Criteria in Subgroups (ITD Population)	Х	
20	Concordance of $\Delta TUV_{global[5w]}$ Bucketing and Week 24 Clinical Improvement Criteria in Subgroups (PP Population)	X	
21	Concordance of Qualitative Assessment of Tc 99m Tilmanocept Imaging and Week 12 Clinical Improvement Criteria (ITD Population)	Х	Х

Table No.	Table Title	Included in Final Tables	Shown in Appendix B
22	Concordance of Qualitative Assessment of Tc 99m Tilmanocept Imaging and Week 12 Clinical Improvement Criteria (PP Population)	X	_
23	Concordance of Qualitative Assessment of Tc 99m Tilmanocept Imaging and Week 24 Clinical Improvement Criteria (ITD Population)	Х	
24	Concordance of Qualitative Assessment of Tc 99m Tilmanocept Imaging and Week 24 Clinical Improvement Criteria (PP Population)	X	
25	Concordance of Qualitative plus Quantitative Assessment of Tc 99m Tilmanocept Imaging and Week 12 Clinical Improvement Criteria (ITD Population)	Х	
26	Concordance of Qualitative plus Quantitative Assessment of Tc 99m Tilmanocept Imaging and Week 12 Clinical Improvement Criteria (PP Population)	Х	
27	Concordance of Qualitative plus Quantitative Assessment of Tc 99m Tilmanocept Imaging and Week 24 Clinical Improvement Criteria (ITD Population)	X	
28	Concordance of Qualitative plus Quantitative Assessment of Tc 99m Tilmanocept Imaging and Week 24 Clinical Improvement Criteria (PP Population)	X	
29	Kendall Rank Correlation of Δ TUV, Δ CDAI, Δ ACR Response Criteria Components, and Δ DAS28 with Δ TUV at 5 weeks (ITD Population)	X	X
30	Kendall Rank Correlation of Δ TUV, Δ CDAI, Δ ACR Response Criteria Components, and Δ DAS28 with Δ TUV at 5 weeks (PP Population)	X	
31	Kendall Rank Correlation of Δ TUV, Δ CDAI, Δ ACR Response Criteria Components, and Δ DAS28 with Δ TUV at 12 weeks (ITD Population)	Х	X
32	Kendall Rank Correlation of Δ TUV, Δ CDAI, Δ ACR Response Criteria Components, and Δ DAS28 with Δ TUV at 12 weeks (PP Population)	Х	
33	Kendall Rank Correlation of \triangle CDAI, \triangle ACR Response Criteria Components, and \triangle DAS28 with \triangle TUV at 24 weeks (ITD Population)	X	X
34	Kendall Rank Correlation of \triangle CDAI, \triangle ACR Response Criteria Components, and \triangle DAS28 with \triangle TUV at 24 weeks (PP Population)	Х	
35	Summary of Generalized Linear Mixed Model to Asses the Additive Effect of either Quantitative or Qualitative assessment of Tc 99m Tilmanocept Imaging on Patient Response Status at Week 12 (ITD Population)	Х	Х
36	Summary of Generalized Linear Mixed Model to Asses the Additive Effect of either Quantitative or Qualitative assessment of Tc 99m Tilmanocept Imaging on Patient Response Status at Week 12 (PP Population)	X	
37	Summary of Generalized Linear Mixed Model to Asses the Additive Effect of either Quantitative or Qualitative assessment	Х	

Table		Included in Final	Shown in Appendix
NO.	of Tc 99m Tilmanocept Imaging on Patient Response Status at	Tables	В
38	Summary of Generalized Linear Mixed Model to Asses the Additive Effect of either Quantitative or Qualitative assessment of Tc 99m Tilmanocept Imaging on Patient Response Status at	X	
39	Week 24 (PP Population) Number and Percentage of Patients with TEAEs (Safety Population)	x	X
40	Summary of TEAEs (Safety Population)	Х	Х
41	Number and Percentage of Patients with TESAEs (Safety Population)	Х	Х
42	Number and Percentage of Patients with TEAEs by Severity Grade (Safety Population)	Х	Х
43	Number and Percentage of Patients with TEAEs by Level of Relationship to Tc 99m Tilmanocept (Safety Population)	Х	Х
44	Serum Chemistry Clinical Laboratory Parameters Summary Statistics (Safety Population)	Х	Х
45	Hematology Clinical Laboratory Parameters Summary Statistics (Safety Population)	х	
46	Urinalysis Clinical Laboratory Parameters Summary Statistics (Safety Population)	Х	
47	Serum Chemistry Clinical Laboratory Parameters Shift Table (Safety Population)	Х	Х
48	Hematology Clinical Laboratory Parameters Shift Table (Safety Population)	Х	
49	Urinalysis Clinical Laboratory Parameters Shift Table (Safety Population)	Х	
50	ECG Parameters Summary Statistics (Safety Population)	Х	X
51	ECG Shift Table (Safety Population)	Х	Х
52	Vital Signs Summary Statistics (Safety Population)	X	Х

Figure No.	Figure Title	Included in Final Figures	Shown in Appendix B
Fig1	Plot of ∆TUV _{global} by Imaging Time Point and ACR20 (ITD Population)	X	X
Fig2	Plot of ∆TUV _{global} by Imaging Time Point and ACR50 (ITD Population)	X	
Fig3	Plot of ∆TUV _{global} by Imaging Time Point and ACR70 (ITD Population)	Х	
Fig4	Plot of ∆TUV _{global} by Imaging Time Point and CDAI (ITD Population)	Х	
Fig5	Plot of ∆TUV _{global} by Imaging Time Point and DAS28 (ITD Population)	Х	
Fig6	Sensitivity Analysis #1 – Tipping Point Analysis to Assess the Appropriateness of Imputation of Clinical Status at Week 24 (ITD Population)	X	Х

Figure No.	Figure Title	Included in Final Figures	Shown in Appendix B
Fig7	Sensitivity Analysis #2 – Tipping Point Analysis to Assess the Appropriateness of Imputation of TUV Prediction (ITD Population)	Х	

Listing No.	Data Listing Title	Included in Final Listings	Shown in Appendix B
	Patient Disposition Data Listing	x	X
	Inclusion/Exclusion Data Listing	X	X
DL3	Protocol Deviations Data Listing	X	X
DL4	Demographics Data Listing	X	X
DL5	Patients Excluded from ITD Population Data Listing	X	X
DL6	Patients Excluded from PP Population Data Listing	X	X
DL7	Patients Excluded from Safety Population Data Listing	X	X
DL8	Medical History Data Listing	X	X
DL9	Prior and Concomitant Medications Data Listing	Х	Х
DL10	Prior and Concomitant RA Medications Data Listing	Х	Х
DL11	Adverse Events Data Listing	Х	Х
DL12	Patient Laboratory Profiles – Hematology Data Listing	Х	Х
DL13	Patient Laboratory Profiles – Serum Chemistry Data Listing	Х	
DL14	Patient Laboratory Profiles – Urinalysis Data Listing	Х	
DL15	Patient Laboratory Profiles – Rheumatology Panel Data	Х	
DL16	Physical Exam Data Listing	Х	Х
DL17	ACR/EULAR 2010 Classification Data Listing	Х	Х
DL18	ACR Data Listing	Х	Х
DL19	CDAI, DAS28, HAQ-DI, and WPI Scores Data Listing	Х	Х
DL20	DAS28 by Joint Data Listing	Х	Х
DL21	DAS28 by Patient Data Listing	Х	Х
DL22	Vital Signs Data Listing	Х	Х
DL23	ECG Parameters Data Listing	Х	Х
DL24	Study Drug Administration Data Listing	Х	Х
DL25	Post-Injection Imaging Data Listing	Х	Х
DL26	SPECT/CT Reader Results Data Listing – Hands and Wrists	Х	Х
DL27	TUV Data Listing	Х	Х
DL28	Qualitative Assessment Data Listing	X	Х
DL29	Qualitative plus Quantitative Assessments which differ from Original Quantitative Assessment	X	X
DL30	ACR Response Criteria Data Listing	Х	Х

